osteochondral changes. Numerous scales have been developed over the years (Denver score is a progressive score, European score is an additive score, Compatible score is a combined Denver and European score, IPSG score is currently the standard). While more sensitive for soft tissue changes, MRI is costly, not-easily assessable, takes a significant time commitment and necessitates sedation in children. Thus MRI is difficult to incorporate in the assessment of acute/bleeding and chronically changing joint.

More recently, musculoskeletal ultrasound (MSKUS) has been used for diagnosis of joint disease in hemophilia. Like MRI, it can reveal joint effusion, proliferation of synovium and subtle cartilage and bone abnormalities. It is the imaging modality recommended by the American College of Rheumatology and is superior to physical exam, especially when evaluating synovitis [Foltz 2012, McAlindon 2012, Porta 2012]. It has been demonstrated that ultrasound helps in the correct and timely diagnosis of acute bleeding episodes [Ceponis 2013], along with other musculoskeletal changes in people with hemophilia [Kidder 2015]. Advantages of MSKUS are its wide availability and low cost. Ultrasound will allow more thorough longitudinal joint assessment [Aznar JA 2015], assisting in the prevention of disease progression, thereby potentially improving outcomes and decreasing cost. Soft-tissue changes such as synovial hypertrophy, which precede joint disease, especially can be effectively diagnosed. Standardized and simplified ultrasound scanning protocols for early arthropathy detection in ankles, knees, and elbows have been published [Martinoli 2013]

Research Question

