Knowledge pertaining to the progression of hemophilic arthropathy of patients with Hemophilia B is limited since Hemophilia B is very rare. Only 1 in 25,000 live male birth is affected compared to patients with Hemophilia A, born at a ratio of 1:5000 male birth (ref). To date, and to the best of our knowledge, there are no prospective studies available to document the development of hemophilia arthropathy in patients with Hemophilia B. We therefore propose to study longitudinal joint changes in patients with moderate and severe Hemophilia B. Most patients are on episodic or prophylactic FIX replacement therapy, whereby patients have a choice to be treated with newer extended half-life (EHL) products or to remain on traditional short-acting FIX products. For example, recombinant FIX albumin fusion protein (rIX-FP) is the most recently approved EHL concentrate and has demonstrated an increase in circulating half-life and area of the curve (AUC) of greater than fourfold versus unmodified FIX. When infused weekly this kinetic profile allows for potential trough levels of greater than 10% [Santagostino 2016]. Such improvement in minimum trough levels could improve the incomplete protection observed with previous products. This study will test the hypothesis that an EHL FIX product (such as rIX-FP) could offer better protection than previous treatment concentrates. The primary research question is whether EHL-rIX with an intended trough level of >5% will improve the outcome of joint health of elbow, ankle and knee joints as assessed with ultrasound assessment in severe hemophilia B patients.

Study Design

Prospective, non-randomized controlled study, whereby patients will be included in 1 of 3 groups depending on their current treatments as outlined below. Patients will be assigned to a specific group by the clinician/PI based on their current regimen with the intent to stay on this regimen for the next 3 years.

- Group A - episodic treatment with FIX concentrates for bleeding episodes
- Group B - prophylaxis using any FIX concentrate with an intended trough of 1-5%
- Group C – prophylaxis with an extended half-life FIX with an intended trough of > 10%

[figure not shown]
Primary Outcome

Joint health status in all 3 groups as assessed by MSKUS at 3 years.

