Joint health will be assessed in all 6 major joints (elbows, knees and ankles), if possible, but at a minimum, target joints and the contra lateral joint will be included. During the exam the previously described Martinoli transducer positions will be used [Martinoli 2013]. To verify MSKUS, the first 10 patients will have parallel x-rays and MRI of the target joint and contra lateral joint.

Allocation of a comparison score of the MSKUS at baseline vs. year 3 will be done by a central, blinded person once all MSKUS images are available. The Joint Activity and Damage Exam (JADE) protocol will be documented to inform scoring. The scoring will be as follows:

MSKUS Assessment	Score
MSKUS imaging indicated improved joint status (decreased signs of arthropathy)	-1
MSKUS imaging indicated no change in joint status	0
MSKUS imaging indicated worsened joint status (increased signs of arthropathy)	+1

Secondary outcomes

- Observational assessment of joint and overall health status evaluated by activity level, functional assessment, pain assessment, joint examination, and adherence.
- Observational assessment of joint health at 1 and 2 years in the different groups
- Observational assessment of MSKUS findings during acute events/bleeding with an opportunity to follow longitudinally to gain understanding of natural evolution of bleeding on MSKUS
- Exploration of potential biomarkers for joint health

Patient Population

Inclusion Criteria

- Male gender
- Severe hemophilia B (factor IX < 1%)
- Age \geq 16 year
- Either on demand or on prophylaxis with rFIX or EHL-rIX products with the intention to stay on the current regimen for the next 3 years
- For Group C start of this treatment regimen up to 6 months ago is permissible
- Willing and able to give written informed consent/assent
- Willing to undergo MSKUS and /or collection of blood sampling for biomarkers

Exclusion Criteria

- Other known bleeding disorder
- Other rheumatologic disorder affecting joints
- Other known neuromotor defect (making physical exam difficult)

Assessment at baseline and at annual exams: Patients will be consented and eligibility will be confirmed. The following will be collected:

- Baseline Form (Demographics, bleeding history, use of hemostatic agents, past medical/surgical history, vital signs)
- Rapid Assessment of Physical Function (RAPA – 1 page questionnaire) to assess physical activity level

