- Hemophilia Activity List (HAL – 3 page self –administered questionnaire) and Time up and go (TUG – assessed by PT) to assess function
- VERITAS-Pro (24 question self-administered questionnaire) for Arm B and C to assess adherence to prophylaxis
- Brief Pain Inventory (BPI – 10 question self-administered questionnaire)
- Joint Assessment (Hemophilia Joint Health Score =HJHS)
- MSKUS: Full J.A.D.E. Protocol (prior exams up to 3 months are permissible)
- x-rays and MRI (first 10 patient only prior exams up to 3 months are permissible)
- Treatment Plan prescribed at visit
- Labs: Factor XI level, FXI inhibitor, hsCPR
- Plasma Sample for biomarkers for Bio Repository

Historical assessments up to 1 year will be allowed as long as all required data was collected.

Assessment of painful episodes: Patients participating in this study will be encouraged to come in for an assessment during a painful episode of either of their elbows, knees or ankles. They will be asked to classify the episode as a bleed vs. non-bleed. The pertinent joint will be examined by a healthcare practitioner as classified to be a bleed vs. non-bleed by the practitioner and a treatment will be determined according to the exam. The patient then will undergo MSKUS and the treatment plan will be reviewed. If changes are made based on the MSKUS findings, they will be noted. The patient is offered to have a sample for the biomarker repository drawn.

Assessment post-painful episodes: Patients who came in for a painful episode are encouraged to return to clinic in 1-2 weeks for repeat exam and MSKUS. The patient is offered to have a sample for the biomarker repository drawn.

Assessment Schedule:

	Baseline	Acute Pain Event	Post-Pain Event	Year 1,2	Year 3
Demographics (age, race/ethnicity)	X			X	X
History (including bleeding history, medications, hemostatic agents and regimen, surgeries, joint bleeding/injury/surgery)	X	X	X	X	X

Recent joint bleeding/injury history (over the last 1 year)	X			X	X
Activity level (e.g RAPA or fitbit)	X	X	X	X	X
Functional assessment (HAL)	X	X	X	X	X
Brief Pain Inventory	X	X	X	X	X
Physical Exam	X	X	X	X	X
HJHS	X	X	X	X	X
MSKU	X	X	X	X	X
Biomarkers	X	X	X	X	X
X-ray (1 st 10 patients only)	X			X*	
MRI (1 st 10 patients only)	X			X*	
Time to up and go	X	X (if appropriate)	X (if appropriate)	X	X
Veritas or Veritas-Pro - Adherence	X	X	X	X	X

*Year 1 only

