Cost to the patient: This study will cover the cost for the MSKUS performed, the x-ray and MRI validation exams for the first 10 patients. It will not cover the cost of the clotting factor and routine clinical laboratory.

Patient compensation: The patient will be compensated for his time for the baseline, year 1, year 2, year 3, acute pain episode and pain follow-up visit at \$150.-/visit. Patients are allowed to get evaluation for more than 1 pain episode and data can be included in the analysis, but there is no compensation for these additional visits. There will also be up to \$50.-/visit in travel compensation for the baseline, year 1, year 2, year 3, and one acute pain episode and pain follow-up visit.

Statistical Plan

For first 10 patients do MRI, compare Ultrasound to MRI and X-ray at baseline and 1 year; and compute sensitivity and specificity and evaluate the rate of false negatives by ultrasound, with MRI as gold standard.

The primary outcome will be proportion of patients with improvement (compared to same or worse) between groups B and C, with analysis by Fisher's Exact Test. Given a feasible sample size of 20 patients per arm for groups B and C, we anticipate having 80% power to detect a 5-fold increase in the proportion of patients classified as improved (e.g., from 10% to 50%). Proportions in each group classified as worse, same, or improved will also be reported and compared by Fisher's Exact Test.

Sample Size

- Arm A: 10 patients
- Arm B: 20 patients
- Arm C: 20 patients

Potential Study Sites

- Washington Center for Bleeding Disorders at Bloodworks NW, Seattle, WA
- Hemophilia and Thrombosis Treatment Center, University California, San Diego, CA
- Seattle Children's Hospital, Seattle, WA
- Orthopedic Hemophilia Treatment Center, Los Angeles, CA
- Tulane University, New Orleans, LA
- Hemophilia and Thrombosis Center, Denver, CO
- Center For Inherited Blood Disorders, Irvine, CA
- Children's Hospital of Michigan, Detroit, MI
- Oregon Health & Science University, Portland, OR

References

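### Groups B and C follow current regimen, yet the primary B vs C Fisher test makes no allowance for the baseline joint findings on which the chance of improving depends

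*Combined protocol and SAP*

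**What the plan says.** - **Allocation (Study Design).** The study is non-randomised. "Patients will be assigned to a specific group by the clinician/PI based on their current regimen".
- **Endpoint (Primary Outcome).** A central, blinded reader compares year 3 with baseline. The score of -1 is defined as "MSKUS imaging indicated improved joint status (decreased signs of arthropathy"; the other scores are 0 for no change and +1 for worse. On how the score is reached, the plan says: "The Joint Activity and Damage Exam (JADE) protocol will be documented to inform scoring".
- **Primary analysis (Statistical Plan).** Improved vs same or worse is compared "between groups B and C, with analysis by Fisher's Exact Test". The three-category comparison also uses Fisher's exact test. Neither analysis has a covariate, stratum, matching rule or adjusted sensitivity analysis, and none appears elsewhere.
- **Baseline data (assessments at baseline and annual exams).** The list includes "MSKUS: Full J.A.D.E. Protocol (prior exams up to 3 months are permissible", together with HJHS and bleeding history.
- **Eligibility (Inclusion Criteria).** No level of baseline joint damage is required or excluded. One rule applies to a single group: "For Group C start of this treatment regimen up to 6 months ago is permissible".
- **Joints (MSKUS Assessment).** The primary analysis needs, at baseline and year 3, at least an acute or historical target joint and its contralateral joint.

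**The concern.** Without randomisation, nothing makes B and C alike at baseline. The endpoint is sensitive to this. A patient whose analysed joints show no signs of arthropathy can score only 0 or +1. One whose only signs are late bony change is unlikely to score -1, since the Background describes the bony damage that x-ray scores reflect as irreversible. Ultrasound could show who has room to improve: according to the Background, "it can reveal joint effusion, proliferation of synovium and subtle cartilage and bone abnormalities". The plan collects this examination at baseline but uses it in no between-group comparison.

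At stake is the study's main question, whether the extended half-life regimen protects joints better. If the groups start with different room to improve, the crude test mixes that difference with any effect of regimen.

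**Working it through.** **Inputs from the plan.** 20 patients each in B and C; 10% vs 50% improved; 80% power; Fisher's exact test (all from the Statistical Plan). Alpha and sidedness are not stated; I assume two-sided 0.05. No baseline distribution is given, so every imbalance below is hypothetical.

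**The plan's own figure.** Pooled normal approximation: z = [0.4 × √20 − 1.96 × √(2 × 0.3 × 0.7)] / √(0.1 × 0.9 + 0.5 × 0.5) = (1.789 − 1.270) / 0.583 = 0.89, which gives 81.3% power. The stated 80% is therefore reproduced by the approximation. Exact enumeration of the Fisher test itself gives 74.2%, and that is the reference value below.

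**Model.** Let h be the share of a group able to improve and r the improvement probability among them; the others cannot improve. The group's crude rate is h × r.

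**1. Hiding a difference.** Take h = 90% in B. For 10% vs 50% at equal mix, r = 0.10/0.90 = 1/9 in B and 0.50/0.90 = 5/9 in C. Hold these fixed and lower h in C:

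| C able to improve | Crude rate in C | Fisher power |
|---|---|---|
| 90% | 0.9 × 5/9 = 50.0% | 74% |
| 80% | 0.8 × 5/9 = 44.4% | 61% |
| 70% | 0.7 × 5/9 = 38.9% | 46% |
| 50% | 0.5 × 5/9 = 27.8% | 20% |

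**2. Creating a difference.** No true effect; the same r in both groups:

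| Able to improve, B vs C | r | Crude rates | Fisher rejection |
|---|---|---|---|
| 70% vs 90% | 20% | 14% vs 18% | 2.8% |
| 70% vs 90% | 50% | 35% vs 45% | 5.4% |
| 50% vs 90% | 20% | 10% vs 18% | 5.2% |
| 50% vs 90% | 50% | 25% vs 45% | 17.9% |

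For comparison, balanced groups give 1.2% at 10% vs 10% and 2.4% at 25% vs 25%.

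**3. What stratification recovers.** Power of an exact conditional test stratified by a binary marker of room to improve, same effect as in step 1, two-sided p-value by probability ordering. The last two columns give the marker's sensitivity and specificity, assumed equal in B and C:

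| C able to improve | Crude | Perfect | 90/90 | 80/80 |
|---|---|---|---|---|
| 90% | 74% | 79% | 78% | 77% |
| 70% | 46% | 73% | 64% | 57% |
| 50% | 20% | 65% | 48% | 36% |

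At 80% of C, an 80/80 marker gives 67% against 61% crude. For the 17.9% false-positive case, stratifying gives 3.0%, 6.7% and 11.9% for the perfect, 90/90 and 80/80 markers.

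The p-value rule matters. With a doubled one-sided p-value, the perfect marker keeps 67% and 56% (70% and 50% of C able to improve), 90/90 keeps 58% and 40%, and 80/80 keeps 51% and 29%. At balance, the doubled rule gives about 72% to 74%.

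**4. HJHS as stratifier.** These are simulated results for a split at the pooled median, with a score equal to joint state plus noise. False positives are for 50% vs 90% able to improve at r = 20% and 50%; power is for 70% and 50% of C able to improve.
- Patients without room at both ends of the score: 6.0% and 19.0% false positives; 48% and 22% power. This is almost no recovery.
- All at one end: 4.3% and 9.5% false positives; 55% and 41% power. This is close to the 80/80 ultrasound marker (4.7% and 11.9%; 57% and 36%).

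**The case against.** - **Each patient is his own control and the reader is blinded.** This limits reader bias and takes account of the starting level. It does not equalise the chance of scoring -1, so the concern stands.
- **The imbalances are invented.** Correct, and the target-joint requirement makes patients without signs less likely. It does not exclude them, because the target joint may be historical. At a 10-point gap the loss is moderate (74% to 61%).
- **The false-positive risk is slight.** This largely stands. A reader might infer that the unadjusted test is likely to yield a spurious advantage for Group C. The documents do not support that: they give no direction, and the 17.9% needs both an extreme split and a 25% rate in B that the plan does not state.
- **HJHS would serve as well.** A reader might infer that HJHS should be ruled out as a stratifier. The documents do not support that either. The Background calls ultrasound "superior to physical exam, especially when evaluating synovitis", a reason to prefer it as first choice, but how HJHS performs depends on where patients without room fall on the score.
- **The marker is itself uncertain.** This stands. The documents nowhere say that effusion or synovial hypertrophy is reversible, and do not say that site operators are blinded to regimen.
- **A stratified sensitivity analysis would be enough.** With so few events this is a defensible alternative, provided it is prespecified.

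**Conclusion.** The point holds as a gap in the analysis plan that is cheap to narrow. Allocation by regimen, an unadjusted primary test and an endpoint that depends on baseline findings are all on the face of the document. The firmer consequence is loss of power: from 74% to 61%, 46% or 20% as the share of C able to improve falls from 90% to 80%, 70% or 50%. False positives matter only at the extreme corner. All figures assume two-sided 0.05, complete follow-up, no improvement in patients without room, and baseline splits that the documents do not supply.

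A reader might go further and infer that the comparison is invalid, or that stratifying would make it causal. Neither follows: no imbalance has been shown, and adjustment on one imperfect marker is partial and leaves unmeasured confounding.

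**What to change.** Prespecify, for example:

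*Improved vs same/worse is compared between B and C by an exact conditional test, with the two-sided p-value by probability ordering. The test is stratified by presence vs absence of soft-tissue findings (such as effusion or synovial hypertrophy) in the target joint and its contralateral joint at the baseline JADE examination. The variable is locked before any year-3 image is scored. The unadjusted Fisher's exact test is reported beside it.*

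The two joints are the minimum set required of every patient in the primary analysis, so the marker does not depend on how many joints were scanned. Take it from the same baseline examination that the central reader compares with year 3. Say which of the two tests carries the primary conclusion; under probability ordering the stratified test loses no power at balance (77% to 79% against 74%). Tabulate baseline JADE findings, HJHS and time on regimen by group, allow HJHS as a sensitivity stratifier, and describe the result as an association.

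Costs and limits:
- The text change is small. The JADE examination is already required, but the plan does not say that sites record presence or absence, so a data field may be needed.
- About 12 improved patients are expected (20 × 10% + 20 × 50%), which allows only one stratifier.
- The site reading is imperfect and may err differently in B and C.
- Group C's baseline may already reflect up to 6 months on regimen.
- The central score may draw on up to six joints, the marker on two.
- The investigators must confirm that soft-tissue findings mark room to improve.

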MSKUS Assessment: MSKUS will be performed by a qualified person at each study site. To reduce operator dependence of results and ascertain uniform data collection, this person must have had sufficient training (took a course on hemophilia related MSKUS though [name], through UCSD, or equivalent). Preferably, the MSKUS is performed by the same person at each time point. Assessment at each time point should be of bilateral elbows, knees and ankles, if possible – at a minimum, MSKUS of an acute or historical target joint (elbow, knee or ankle) and the contralateral joint has to be performed at baseline and at 3 years to be included in primary endpoint analysis.

X-ray Assessment: The 1st 10 patient in the study will have x-rays of their target joint and contralateral joint using the following views:

- Knee – radiographs: standard AP and lateral, but also include a merchant view (3 views total)
- Elbow – radiographs: standard AP and lateral (2 views)
- Ankle – radiographs: standard AP, lateral, and mortise (3 views)

x-ray studies done within 6 months of study visit are permissible.

MRI Assessment: The 1st 10 patient in the study will have MRI images of their target joint and contralateral joint using the following protocol:

Preferably imaging should occur on a 3 Tesla machine and each site will have their own standard clinical MRI protocols using conventional 2D sequences in 3 imaging planes (typically fast spin echo [FSE]). In addition, add a sagittal 2D gradient echo sequence (to better visualize hemosiderin deposits) and also a 3D sequence. The 3D sequences are depending on particular MRI vendor at the individual sites. If available a 3D FSE should be performed (GE has CUBE, Siemens has SPACE, Philips has VISTA, Hitachi has isoFSE, and Toshiba has 3D MVOX). Acquisition for the 3D sequence should be in the sagittal plane and voxel size should be close to isotropic. The 3D sequence will be very useful for comparing specific planes with ultrasound (such as the femoral trochlea). The radiology consultant for this study will advise on sequencing at each individual site.

MRI studies done within 6 months of study visit are permissible.

Biomarker Repository: During all visits, including acute pain and pain follow-up visits, the patient will be approached to contribute blood samples for the repository. Five citrated (blue top) tubes will be drawn, samples will be spun, aliquoted and frozen for potential later studies.

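### The 80% power claim counts all 20 planned patients per arm, but the primary analysis takes only those scanned at baseline and year 3, and no loss is allowed for

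*Combined protocol and SAP*

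**What the plan says.** The Statistical Plan compares the proportion improved between groups B and C, "with analysis by Fisher's Exact Test". It justifies the size in one sentence: "Given a feasible sample size of 20 patients per arm for groups B and C, we anticipate having 80% power" for a five-fold increase, with 10% rising to 50% as the example. The Sample Size list repeats the same number: "Arm B: 20 patients" and "Arm C: 20 patients".

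The Primary Outcome section sets the endpoint as "Joint health status in all 3 groups as assessed by MSKUS at 3 years". The MSKUS Assessment section then decides who is analysed. Ultrasound of a target joint and the joint on the opposite side "has to be performed at baseline and at 3 years to be included in primary endpoint analysis".

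The documents give no significance level, no sidedness, no expected loss over the 3 years, no enrolment above 20, no replacement rule and no method for a patient without a year-3 scan.

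**The concern.** The number in the power sentence is also the number planned, whereas the number analysed is those who have both scans 3 years apart. Every patient without a usable year-3 scan reduces the evaluable count below 20, and nothing in the plan makes up for it. This lowers power even if loss is completely at random; whether loss is related to outcome is a separate question.

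What is at stake is how the result is read. A non-significant B versus C comparison would be taken to come from an 80%-powered test when the test actually run may have clearly less. Hemophilia B is very rare by the protocol's own account, so the comparison would be hard to repeat.

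**Working it through.** **Inputs from the documents:** 20 per arm; p_B = 0.10 and p_C = 0.50 (the plan's example); Fisher's exact test; both scans required. **Assumed, because not stated:** alpha 5%, tried two-sided and one-sided; loss of 5% to 20% over 3 years, the same in both arms and independent of outcome.

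**Step 1. Reproduce the 80%.** Two-sided pooled normal approximation, no continuity correction, with p̄ = 0.30:

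Power = Φ{ [|p_C − p_B| − 1.96·√(2p̄(1−p̄)/n)] / √([p_B(1−p_B) + p_C(1−p_C)]/n) }

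At n = 20: [0.40 − 1.96·√(0.42/20)] / √(0.34/20) = (0.40 − 0.2840)/0.1304 = 0.89, and Φ(0.89) = 81.3%. Solving the same formula for 80% gives n = 20 per arm. This is a plausible source of the claim, but it is not the planned test. A one-sided continuity-corrected approximation also gives n = 20 (80.4%).

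**Step 2. The planned test with all 20 evaluable.** Enumerate every pair (x_B, x_C), keep the pairs with Fisher p ≤ 0.05, and sum Bin(x_B; 20, 0.10) × Bin(x_C; 20, 0.50). For example, two-sided rejection in favour of C needs x_C ≥ 5 when x_B = 0, ≥ 7 when x_B = 1, ≥ 9 when x_B = 2 and ≥ 10 when x_B = 3. Results: 74.2% two-sided and 83.7% one-sided.

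**Step 3. Loss.** Let the evaluable number in each arm be Bin(20, 1 − d), independently, and average the exact power over both arms.

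| Loss d | Fisher, two-sided 5% | Fisher, one-sided 5% |
|---|---|---|
| 0 | 74.2% | 83.7% |
| 5% | 74.4% | 80.3% |
| 10% | 71.4% | 77.8% |
| 15% | 68.0% | 74.7% |
| 20% | 64.4% | 71.2% |

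The flat two-sided figure from 0 to 5% is no error. Fisher power is discrete and does not fall steadily with n; 20 in B and 19 in C gives 79.7%. No two-sided combination from 8 to 20 per arm reaches 80%.

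The Step 1 approximation at fixed equal arms gives 79.2% at 19, 76.8% at 18 and 71.4% at 16.

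**Step 4. Detectable rate.** Group C rate needed for 80% Fisher power against 10% in Group B, equal arms:

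| Evaluable per arm | Two-sided 5% | One-sided 5% |
|---|---|---|
| 20 | 53% | 48% |
| 18 | 57% | 51% |
| 16 | 61% | 55% |

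**The case against.** - **A small loss need not break the claim.** A reader might infer that 80% requires zero loss, or that any realistic loss defeats it. The documents do not support this. With one-sided Fisher, 19 per arm still gives 81.4%, and 5% random loss averages 80.3%. With two-sided Fisher, 80% is missed with nobody lost. No loss rate is given against which 10–20% could be called realistic. This objection stands, and it limits the point to losses of about 10% or more on the one-sided reading.
- **Loss is not the whole gap.** A reader might put the entire drop from 80% to 64% down to missing scans. On the two-sided reading, about 6 points (80 − 74.2) come from the test and alpha before anyone is lost. Loss of 10% removes a further 2.8 points (74.2 − 71.4), and 20% removes 9.8 (74.2 − 64.4). This also stands, so the two must be reported separately.
- **Equal-arm figures look too bleak.** Two-sided power is 66.8% at 18/18 and 58.1% at 16/16, below the random-loss averages of 71.4% and 64.4%. The averages are the fairer summary of power under loss.
- **Twenty may mean evaluable patients, and retention is supported.** The figure is called feasible, patients must intend to keep their regimen for 3 years, and the scheduled visits are compensated with travel support. None of this guarantees a year-3 scan. The inclusion criteria also accept willingness for ultrasound and/or blood sampling, so a patient could enter without agreeing to the scans. If 20 evaluable was meant, the plan does not say so and gives no larger enrolment figure.

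**Conclusion.** The point holds as a mismatch between the number in the power sentence and the number the analysis rule will produce, with no allowance linking them. Its size depends on three things the plan leaves open: alpha, sidedness and loss.

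At two-sided 5%, the planned test does not reach 80% at 10% versus 50% even with full follow-up, and loss of 10–20% brings it to about 71–64%. At one-sided 5%, 80% survives a loss of about 5% but not 10% or more (about 78–71% at 10–20%). On the approximation that reproduces the printed figure, power is just under 80% with 19 evaluable per arm and clearly under with 18 or fewer.

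A reader might infer that securing 20 evaluable patients per arm would by itself restore 80%. At two-sided 5% it would not. The evidence supports correcting the power statement; it does not show that the study is too small to run. All figures rest on the example rates and on loss at random.

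**What to change.** Keep 20 per arm. In the Statistical Plan, state alpha and sidedness, state the expected share of patients without a year-3 scan, and give the Fisher power in two steps: all 20 evaluable, then averaged over the expected loss. For example, at two-sided 5%:

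> With 20 evaluable patients per arm, Fisher's exact test (two-sided 5%) has 74% power for 10% versus 50% improved. If 10–20% of patients lack a year-3 scan, power is about 71–64%. For 80% power, about 53% would have to improve in Group C with 20 evaluable per arm, and about 57% and 61% with 18 and 16.

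The sponsor should substitute its own completion rate and chosen alpha. If 20 was meant as the evaluable number, say so and give the enrolment target separately.

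The cost is a few sentences, with no added patients, visits or procedures. The drawback is that the stated power becomes less favourable.

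### With 20 per arm, Fisher's exact test at two-sided 5% has 74% power for 10% against 50% improved, not the stated 80%; alpha and sidedness are not given

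*Combined protocol and SAP*

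**What the plan says.** Under Statistical Plan, the primary comparison is the proportion of patients improved (against same or worse) "between groups B and C, with analysis by Fisher's Exact Test". The size is 20 patients in each of these groups, described as what is feasible and repeated under Sample Size. The plan then says "we anticipate having 80% power to detect a 5-fold increase in the proportion of patients classified as improved (e.g., from 10% to 50", that is, 10% in group B and 50% in group C. No alpha, sidedness, power method or allowance for losses appears anywhere in the document.

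Two other places bear on the claim. Under Research Question, the hypothesis is directional: an extended half-life product "could offer better protection than previous treatment concentrates". Under MSKUS Assessment, a scan of a target joint and "the contralateral joint has to be performed at baseline and at 3 years to be included in primary endpoint analysis", so a patient without a 3-year scan does not count towards the 20.

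**The concern.** The power sentence is the only account of what 20 per arm can detect. Fisher's test is conservative at this size, so a power figure from a normal approximation will usually be too high for it, and 80% looked high for these rates.

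If the true power is lower, the chance of missing the effect the plan itself names is larger than a reader would think, and a non-significant result would be over-read as evidence against that effect. Leaving sidedness open also leaves the rejection rule open. A result of 2/20 against 8/20 has two-sided p = 0.065 and one-sided p = 0.032, so under the plan as written the same data could be called significant or not.

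**Working it through.** **Inputs.** From Statistical Plan: Fisher's exact test, n = 20 per arm, p_B = 0.10, p_C = 0.50, stated power 80%. Assumed, because the plan is silent: alpha 0.05 two-sided, with one-sided alternatives also run.

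**Trying to reproduce 80%.** The pooled normal approximation without continuity correction gives

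power = Φ{(|p_C − p_B| − 1.96·√[2p̄(1−p̄)/n]) / √[(p_B(1−p_B) + p_C(1−p_C))/n]}

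With p̄ = 0.30, the null standard error is √(0.42/20) = 0.1449 and the alternative one is √(0.34/20) = 0.1304. Then (0.40 − 1.96 × 0.1449)/0.1304 = 0.89, and Φ(0.89) = 81.3%. The matching sample-size formula returns exactly 20 per arm. This is close to the stated figure, but it is not the power of the named test. The plan does not say how the 80% was obtained, so this source is only an inference. The arcsine approximation gives 83.5%.

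**Exact power of the named test.** Let X be the number improved in group B, Binomial(20, 0.10), and Y the number in group C, Binomial(20, 0.50). Power is the sum over x of P(X = x) × P(Y ≥ c(x)), where c(x) is the smallest y above x that gives p ≤ 0.05. Rejections in the wrong direction add about 0.0000001.

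| x | P(X = x) | c(x), two-sided 5% | P(Y ≥ c) | Product |
|---|---|---|---|---|
| 0 | 0.1216 | 5 | 0.9941 | 0.1209 |
| 1 | 0.2702 | 7 | 0.9423 | 0.2546 |
| 2 | 0.2852 | 9 | 0.7483 | 0.2134 |
| 3 | 0.1901 | 10 | 0.5881 | 0.1118 |
| 4 | 0.0898 | 11 | 0.4119 | 0.0370 |
| 5 | 0.0319 | 13 | 0.1316 | 0.0042 |
| 6 or more | | | | 0.0005 |
| **Sum** | | | | **0.7424** |

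The same sum at other levels gives 74.2% at one-sided 2.5% and 83.7% at one-sided 5%. The shortfall at two-sided 5% comes from the test's conservatism: its actual type I error at 20 per arm never exceeds 0.025.

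**What would give 80% at two-sided 5%.** With 10% against 50%, 22 per arm gives 78.6% and 23 per arm gives 81.1%. With 20 per arm and 10% in group B, group C needs about 53% (80.3%).

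**Does a 5-fold ratio fix the power?** Fisher, 20 per arm:

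| Group B vs group C | Two-sided 5% | One-sided 5% |
|---|---|---|
| 5% vs 25% | 29.9% | 37.6% |
| 8% vs 40% | 57.6% | 69.5% |
| 10% vs 50% | 74.2% | 83.7% |
| 12% vs 60% | 86.9% | 92.5% |
| 15% vs 75% | 96.6% | 98.4% |

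At two-sided 5%, a 5-fold increase reaches 80% only when the group B rate is about 10.8% or higher.

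**Fewer evaluable patients.** These losses are assumed, because the plan gives no rate. For 10% against 50%:

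| Evaluable per arm | Two-sided 5% | One-sided 5% |
|---|---|---|
| 20 | 74.2% | 83.7% |
| 19 | 70.9% | 81.4% |
| 18 | 66.8% | 78.3% |
| 16 | 58.1% | 70.8% |

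**The case against.** The strongest reply is that the shortfall depends on an assumed level. The hypothesis is directional, and at one-sided 5% the named test gives 83.7%, so the claim would be met. This stands to the extent that 80% is not wrong under every reading. But a directional hypothesis is not a significance level, and the plan does not say that one-sided 5% is meant. On that reading too, the margin is gone with two losses per arm (78.3%).

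A second reply is that the 5-fold phrase is tied to its example and is only loose wording. The plan does give one specific pair, and that pair is what allows a check at all. Still, the pair is offered as an example of a general claim, and the general claim fails under either level: 5% against 25% has 30% or 38% power.

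Third, 20 per arm was set by feasibility in a rare disease, so the design does not turn on the figure. That is true, and it limits the consequence to how the trial is described and read. With n fixed, though, stating correctly what it can detect is the main use of a power sentence.

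Finally, the loss scenarios are illustrations. The plan does not say whether 20 means enrolled or evaluable, and the scenarios show sensitivity, not a further error.

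**Conclusion.** The concern holds. At two-sided 5%, the plan's own test, sample size and rates give 74.2% power, 5.8 points below the stated 80%, so the chance of missing the stated effect is about 26% instead of 20%. This rests on two-sided 5% (or one-sided 2.5%) being the intended level. If one-sided 5% was intended, power is 83.7% and the numerical claim stands for 20 analysed per arm. The absence of alpha and sidedness, and the failure of a fold-change to determine power, do not depend on that assumption. The point should be fixed, but it does not undermine the choice of test or the sample size.

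**What to change.** 1. State alpha and whether the primary test is one- or two-sided. Under Primary Outcome, comparison scoring "will be done by a central, blinded person once all MSKUS images are available", so this can be settled before any primary result exists.
2. If two-sided 5% is meant, replace the power sentence with, for example: *With 20 evaluable patients per arm and Fisher's exact test at two-sided alpha 0.05, power is 74% for 10% against 50% improved and 80% for 10% against 53%; with 18 or 16 evaluable per arm, power for 10% against 50% is 67% or 58%.* If one-sided 5% is meant, say so and give 84%, 78% and 71% for 20, 18 and 16 evaluable per arm.
3. Delete the fold-change and give only specific pairs of rates.

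This rewrites one sentence and adds the significance level. It needs no extra patients and no change to the test. The only cost is a lower stated power if two-sided 5% is chosen.
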